Heart: troponin; Kidney: creatinine, blood urea nitrogen (BUN), electrolytes (calcium, carbon dioxide, chloride, potassium, sodium, magnesium); Pancreas: glucose, HbA1c, lipase; Liver: ALT, AST, ALP, total bilirubin; Muscle weakness: creatinine kinase; Hematology: red blood cell count, hemoglobin, platelet count, prothrombin time (PT), partial thromboplastin time (PTT), ddimer; Immunology: white blood cell count, neutrophils, lymphocytes, monocytes, eosinophils, T cells, SARS-CoV-2 viral load in nasopharyngeal sample, SARS-CoV-2 serology in blood; Inflammation: CRP, ferritin, LDH, caspase-1, IL-18, IL-1β, IL-1 receptor antagonist, gasdermin D, IL-6, TNF-α, G-CSF

- *5a) Analysis and comparison of* surrogate markers of COVID-19 related inflammation and organ involvement as determined by biochemistry, hematology, and immunology labs and studies, in treatment group versus placebo group, respectively, for
 - o values on days 1 (enrollment), 7, 14, 21, 28 post randomization
 - o changes from enrollment to days 7, 14, 21, or 28 post randomization
 - o changes between days 7, 14, 21, 28 post randomization
- *5b) Reference range rates:* proportion of treatment group versus placebo group, respectively, who experience normal / in-range values for a given marker at days 7, 14, 21, 28 post randomization

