All data collected by the Study Team and recorded by the subjects will be entered into the EDC per the schedule of events. OnCore, a Clinical Trial Management System in which subject visits

MOD00008997 IRB Approved 12/23/2021 - 11/9/2022

can be monitored as well as Case Report Forms developed, will be used for this trial. Subjects will be asked to hand in their subject diary during visits on days 7, 14, 21, and 28.

Background Standard of Care

All eligible subjects will receive background standard of care, however there are certain prohibited medications subjects cannot be given while dosed with the IP as outlined in Section 5.4. Background standard of care will be commensurate with disease severity and aligned to standards at the time of the trial. At present, standard of care includes vaccines, antiviral treatment with remdesivir, monoclonal antibodies against SARS-CoV-2, dexamethasone, supplemental oxygen, noninvasive and invasive ventilation, antibiotics, vasopressors, anti-coagulation and ECMO; but this may evolve over the coming months as new therapies or treatments come online including offlabel use of other drugs.

Patients recruited to the study will not be asked to forgo background standard of care in any way. Recruitment will be based on inclusion and exclusion criteria and include individuals evaluated for suspected COVID-19 in a MedStar Urgent care or the Emergency Room setting, and triaged not to need in-hospital care. These individuals have the potential but not the likelihood for hospital admission with worsening COVID-19 disease progression. Current outpatient standard of care includes symptomatic treatment and this will not be altered to the point that analgesics and antipyretics will be held. Patients whose COVID-19 related illness deteriorates to the point that they need ambulatory medical care or hospitalization will remain in the study and medical care as determined by managing physicians will not be subverted in any manner as part of the study. Patient data collection as per study diary and study visits will be maintained for the minimum 60 days and study drug will be provided and monitored for compliance unless there is an indication for discontinuation of study drug, see section on drug discontinuation.

Study Population

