⁵Blood draws: serum and peripheral blood mononuclear cells for later immunological analysis.

- ⁹Day 1 (i.e., the first day of drug intake) is most likely also the screen / enroll day; subjects will receive a phone call from Study Team a few hours after first dose is taken to check up on how they are doing.
- ¹⁰ET: Subjects who prematurely discontinue study drug for any reason are asked to have an Early Termination (ET) visit the day the last study drug dose was taken.
- ¹¹ Subjects will be given a digital thermometer and portable pulse oximeter to record their temperature and oxygenation daily in the provided subject diary.
- ¹² These laboratory tests will be collected at a one-time blood draw at each visit, a total of 5 collections at the 5 visits (Screening, Day 7, Day 14, Day 21, and Day 28). The amount drawn at each timepoint is as follows: Screening visit (56 mL or 11 teaspoons), Day 7 (44 mL or 9 teaspoons), Day 14 (56 mL or 11 teaspoons), Day 21 (20 mL or 4 teaspoons), and Day 28 (48 mL or 10 teaspoons). The early termination visit would be in lieu of one of the in-person visits, it is not included in the total. Laboratory tests collected at the screening/enrollment visit may be collected by a home health agency in the subjects' home.

¹³Chest x-ray or CT of the chest will be completed as standard of care but not required for screening or randomization or enrollment

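### SARS-CoV-2 serology is to be analysed as change from enrollment, but Table 1 schedules no enrollment antibody test

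*Combined protocol and SAP*

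**What the plan says.** Section 3.4, area 5, names "SARS-CoV-2 serology in blood" under Immunology. Endpoint 5a then asks, for the area-5 markers as a group, for "values on days 1 (enrollment), 7, 14, 21, 28 post randomization", for "changes from enrollment to days 7, 14, 21, or 28 post randomization" and for "changes between days 7, 14, 21, 28 post randomization". Endpoint 5b asks for the proportion with "normal / in-range values for a given marker at days 7, 14, 21, 28 post randomization". No marker is exempted. The synopsis repeats these time points.

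In Table 1 (Section 5.2) the row for the antibody test in blood carries marks at day 28 and at the early termination (ET) visit only. Footnote 7 describes it as a quantitative antibody test, leaves the assay method open and gives no time points. Footnote 5 covers a separate row, marked at screening/enrollment, under which serum and mononuclear cells are stored for later immunological work. No antibody assay on that serum is specified. Section 8.5 analyses change in continuous endpoints with mixed effects models for repeated measures.

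Section 5.1 states that "standard of care includes vaccines, antiviral treatment with remdesivir, monoclonal antibodies against SARS-CoV-2" and other measures. Section 5.3 does not exclude prior vaccination or prior infection.

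**The concern.** A change from enrollment needs an enrollment value, and the schedule does not provide one for serology. If the plan is followed as written, the change analyses for this marker have no data, and the Section 8.5 repeated-measures model has one scheduled value per subject.

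What remains is the day-28 titre. Vaccination and anti-SARS-CoV-2 antibodies are both permitted background care, so a high day-28 titre may reflect the current infection, earlier immunity or infused antibody. Without an enrollment value these cannot be told apart. The trial also lacks a planned enrollment antibody measurement as a baseline covariate. Section 8.7 says the study's purpose is to supply an effect-size estimate for a larger trial. For antibody response, the schedule as written cannot supply one.

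**Working it through.** **The plan's own figure.** No sample-size figure concerns serology. The only one, in Section 8.7, is a rate-ratio difference of over 60% for 80% power with 20 per arm. With a Wald test on the log rate ratio (two-sided 5%), the control events per subject needed are (1.960 + 0.842)² × (1/20 + 1/(20 × RR)) / (ln RR)². This gives about 2.89 for RR = 1.6 and about 1.64 for RR = 0.4. The plan states no control rate, so the figure can be neither confirmed nor refuted. Nothing below depends on it.

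**Required against scheduled.** Table 1 has 11 columns: screen/enroll, D1, D4, D7, D10, D14, D21, D28, D42, D60, ET. The antibody row's marks fall in columns 8 (D28) and 11 (ET).

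| Quantity for serology | Required by 3.4 | Derivable from scheduled tests |
|---|---|---|
| 5a values (enrollment, 7, 14, 21, 28) | 5 | 1 |
| 5a changes from enrollment | 4 | 0 |
| 5a changes between days 7, 14, 21, 28 | 4 × 3 / 2 = 6 | 0 |
| 5b in-range rates (7, 14, 21, 28) | 4 | 1 |

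An ET test could add a second value for a subject who stops drug early and still attends day 28. It cannot supply an enrollment value.

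**Could another row supply the baseline?**
- The immunology row is marked at screening, but footnote 6 refers to Appendix 12.1 for its contents, and that list has no SARS-CoV-2 antibody test.
- Footnote 12 says "These laboratory tests will be collected at a one-time blood draw at each visit". It is attached to the antibody row but also to the HIV and hepatitis screening tests, so it describes pooling of tubes and does not put every test at every visit.
- Footnote 5 provides stored enrollment serum but plans no assay.

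**Chance imbalance at 20 per arm.** Allocation is 1:1, with no stratification described. Let p be the prevalence of prior immunity, which the documents do not give. The expected arm difference is 0. At p = 50% the SD of the difference is √(2 × 0.5 × 0.5 / 20) = 0.158, or about 16 percentage points. Exact binomial probabilities are:

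| Assumed p | Gap of 20 points or more | Gap of 30 points or more |
|---|---|---|
| 30% or 70% | 0.226 | 0.056 |
| 50% | 0.268 | 0.081 |

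**What a baseline would buy.** For 80% power at two-sided 5%, the detectable day-28 difference is (1.960 + 0.842) × √(2/20) = 0.886 SD. Adjusting for enrollment titre multiplies this by √(1 − ρ²), and a raw change score multiplies it by √(2 − 2ρ), where ρ is the enrollment to day-28 correlation (assumed).

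| ρ | Day 28 alone | Adjusted for baseline | Raw change |
|---|---|---|---|
| 0.3 | 0.886 | 0.845 | 1.048 |
| 0.5 | 0.886 | 0.767 | 0.886 |
| 0.7 | 0.886 | 0.633 | 0.686 |

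Adjustment does better than the raw change at each of these values.

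**The case against.** The strongest reply is that this is a wording mismatch with little behind it. Endpoint 5a applies one visit list to a long set of markers, and others miss it too: swabs are not marked at days 7 or 21, and standard labs are not marked at day 21. Section 7.1 says assessments follow the Schedule of Events, so 5a could be read as covering scheduled visits only. The trial calls itself hypothesis generating, and no primary, safety or stopping analysis uses serology. That stands as a limit on importance. It does not settle the baseline: the swab and standard-lab rows are marked at enrollment, and the antibody row is not.

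The table was read from a PDF with garbled marks, so a lost mark cannot be fully excluded. Against that, 15 of the 16 study-team rows keep their screening/enrollment mark, and the antibody row is the only one without it.

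Three stronger readings are tempting but are not supported:
- **That the day-28 arm comparison is confounded by vaccination or antibody therapy.** Allocation is randomized and double-blind. Immunity and therapy before randomization are balanced in expectation, and later therapy is given under blinding. The cost is variance and chance imbalance. Section 8.3 also summarizes medical history and prior and concomitant medications, where these exposures could be reported.
- **That the blood volumes prove the test is absent at screening.** Footnote 12 gives "Screening visit (56 mL or 11 teaspoons), Day 7 (44 mL or 9 teaspoons" and then 48 mL at day 28, so day 28 is 48 − 44 = 4 mL above day 7. That fits one extra antibody tube, but footnote 4 also puts a pregnancy test at end of treatment. No tube volumes are given, so the totals decide nothing.
- **That the baseline is lost for good, or that a particular antigen must be assayed.** Stored enrollment serum could still be tested, and the documents name no assay, vaccine or antibody target from which to choose.

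**Conclusion.** Section 3.4 and Table 1 disagree on serology and must be reconciled. As scheduled, none of the 10 change quantities in 5a (4 from enrollment, 6 between visits) can be derived trial-wide, and only day 28 is available for values and in-range rates. The day-28 comparison between arms is valid but imprecise, and it does not measure response to this infection.

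This rests on the antibody row of Table 1 being complete as read. The sizes of the chance imbalance and of the gain from adjustment also rest on assumed prevalences of 30% to 70% and assumed correlations of 0.3 to 0.7. The consequence is limited to one exploratory secondary marker. It still merits correction, because a stated analysis cannot be carried out and the repair is small.

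**What to change.** Mark the antibody test at screening/enrollment in Table 1, and state that it is run on the serum already drawn then under footnote 5. Use the same assay for enrollment and day-28 samples, and name it in footnote 7. In Section 3.4 and the synopsis, limit 5a serology to the enrollment value, the day-28 value and the change between them, and limit 5b serology to day 28. In Section 8.5, analyse day-28 titre adjusted for enrollment titre.

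This raises 5a for serology from 1 to 2 values and from 0 to 1 change, and the remaining time points are dropped explicitly. The cost is about 40 added assays (one per subject) and the wording changes, with no extra visit or venipuncture. It assumes that the stored enrollment serum is sufficient for the assay, which the documents do not state.

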4 SAFETY AND TOLERABILITY

The drug in an oral form has been used in nearly one hundred patients without a history of major side effects. During the trial, it is therefore anticipated that no more than 2 subjects out of 20 will have an adverse event of grade 4 or 5 that is probably related to belnacasan (VX-765/RVT-201/MSR-001). In terms of stopping rules, should two or more subjects develop a similar Grade 3 SAE that is at least possibly related to belnacasan or should one or more subjects develop a \geq Grade 4 SAE that is at least possibly related to belnacasan, the trial will be paused for DSMB safety review. Safety Monitoring processes are identified in Section 7.14.

5 STUDY DESIGN

5.1 Study Description

This is a phase 2 proof of concept randomized, double-blind, placebo-controlled trial with the purpose of assessing the safety, tolerability and treatment effect of the orally administered Caspase-1 inhibitor, belnacasan, for the treatment of patients with mild to moderate COVID-19. 20 subjects will be given 900 mg TID of belnacasan and 20 subjects will be given a placebo TID for 28 days, and assessments of safety, tolerability, and treatment effect will be performed for up to 60 days.

At the screening / baseline / day 1 Visit, subjects will provide informed consent and be screened for eligibility based on the Inclusion / Exclusion criteria identified in Section 5.3. Subjects will also receive the first dose of study drug at this visit once study eligibility has been confirmed, and the second dose of study drug will be taken approximately 8-12 hours after the first dose. Study drug will be continued three times daily (morning, mid-day, and nighttime doses) through day 28. Some patients identified will require a PCR-confirmed COVID test, having only had a rapid antigen test. Patients requiring a PCR test can either have one collected with screening labs prior to leaving the MedStar enrollment site or have these labs collected via a home-health research visit at no cost to the potential participant. Prior to study-specific procedures the study team will obtain their consent in-person or by remote consent process. An e-consent platform, Interlace, may also be used to document consent electronically. Once their COVID-19 status is confirmed via PCR they will complete the remainder of their screening/enrollment visit at either MedStar Washington Hospital Center or MedStar Franklin Square within the next 1 to 3 days. The remote consent

process and e-consent will follow MedStar institutional policies and procedures (MG.O-004.06 and MG.O-004.07).

The trial duration will be approximately 60 days (8.5 weeks) for all subjects enrolled. As outlined in the Schedule of Events Table in Section 5.2, over the course of the study duration, all subjects will use a diary to record IP intake as well as symptoms and activity levels with guidance to do so at the same time each day; assess physical parameters using a study-provided thermometer and pulse oximeter for which detailed instructions will be provided at enrollment; be assessed at regular intervals by the Study Team via telephone calls and in-person follow-up clinic visits; and give blood for laboratory tests.

An experienced and appropriately licensed Study Team member will conduct the telephone study visits and be the point of contact if subjects experience deterioration, such as high temperatures (above 38C) or low oxygen saturation levels (below 93%). The primary coordinator of the trial will be a registered nurse, experienced in vital sign and symptom review, with the ability to escalate any medical concerns to the Principal Investigator as it relates to worsening of the subjects' illness or adverse event identification. The Principal Investigator or delegated Sub-Investigator, as documented on the study delegation log, is well-versed in delegation of appropriate tasks as defined by licensure and scope of practice and will work closely with the study team to assure delegation remains appropriate through the duration of the trial. Medical advice or direction will only be given by sufficiently licensed study personnel, either mid-level providers or physicians, in partnership with their primary care team.

Subjects will be instructed to fill in symptoms assessment, overall health assessment, temperature and oxygen saturation levels in the diary each morning; and to note in the diary 3 times per day that they have taken the study drug. The Study Team will conduct in-person visits with the subjects on days 7, 14, 21, and 28 and telephonic visits with subjects on days 1, 4, 10, 42, and 60; as well as when / if subjects contact them due to symptom deterioration as instructed. Subjects will receive reminders to complete the diary via text message and / or email. Subjects who prematurely discontinue study drug for any reason will be asked to have an Early Termination (ET) visit the day the last study drug dose is administered; moreover, they will be encouraged to stay enrolled so that further safety and outcome information can be collected and analyzed.

All data collected by the Study Team and recorded by the subjects will be entered into the EDC per the schedule of events. OnCore, a Clinical Trial Management System in which subject visits

MOD00008997 IRB Approved 12/23/2021 - 11/9/2022

can be monitored as well as Case Report Forms developed, will be used for this trial. Subjects will be asked to hand in their subject diary during visits on days 7, 14, 21, and 28.

Background Standard of Care

All eligible subjects will receive background standard of care, however there are certain prohibited medications subjects cannot be given while dosed with the IP as outlined in Section 5.4. Background standard of care will be commensurate with disease severity and aligned to standards at the time of the trial. At present, standard of care includes vaccines, antiviral treatment with remdesivir, monoclonal antibodies against SARS-CoV-2, dexamethasone, supplemental oxygen, noninvasive and invasive ventilation, antibiotics, vasopressors, anti-coagulation and ECMO; but this may evolve over the coming months as new therapies or treatments come online including offlabel use of other drugs.

Patients recruited to the study will not be asked to forgo background standard of care in any way. Recruitment will be based on inclusion and exclusion criteria and include individuals evaluated for suspected COVID-19 in a MedStar Urgent care or the Emergency Room setting, and triaged not to need in-hospital care. These individuals have the potential but not the likelihood for hospital admission with worsening COVID-19 disease progression. Current outpatient standard of care includes symptomatic treatment and this will not be altered to the point that analgesics and antipyretics will be held. Patients whose COVID-19 related illness deteriorates to the point that they need ambulatory medical care or hospitalization will remain in the study and medical care as determined by managing physicians will not be subverted in any manner as part of the study. Patient data collection as per study diary and study visits will be maintained for the minimum 60 days and study drug will be provided and monitored for compliance unless there is an indication for discontinuation of study drug, see section on drug discontinuation.

Study Population

Urgent Care or Emergency Department presenting subjects, who are not under immediate consideration for inpatient admission and with onset of at least one moderate COVID-19 symptom of less than 7 days, will be assessed for eligibility on the basis of a positive antigen test or reverse transcriptase polymerase chain reaction (RT-PCR) assay for SARS-CoV-2 in a respiratory tract sample on presentation to a MedStar Urgent care or the Emergency Department facility. If only a rapid test is resulted, a home health research visit will be arranged, following consent, to obtain a confirmatory RT-PCR test with initial screening labs.

Page 31 of 66

Enrollment of Diverse Study Population

Recognizing that COVID-19 disproportionately impacts racial and ethnic minorities, the study will seek to enroll a diverse patient population. For example, one of the main trial sites, MedStar Washington Hospital Center, is the largest hospital in the District of Columbia. Its primary service area includes 11 zip codes, most of which are the zip codes that make up Wards 5, 7, and 8. Minorities represent 58% of the population in DC overall, and 69%, 97%, and 96% of the population in Wards 5, 7, and 8, respectively. Three Metrobuses service the campus and MedStar provides free, wheelchair-accessible shuttle buses from two Metrorail stations. Moreover, subjects will receive financial support for travel to and from study visits.

Both in terms of COVID-19 presentation and clinical trial enrollment, communities of color have represented the vast majority of patients at WHC. Specifically, over the last 15 months, nearly 6,000 patients have presented at the WHC emergency department with COVID-19. Of the 97% from whom race / ethnicity data were recorded, 7% were White Non-Hispanic, 67% were Black or African American Non-Hispanic, 21% were Hispanic and 6% were Other (Asian, American Indian, Alaska Native, or more than one race or ethnicity). The MedStar system has enrolled 875 subjects into COVID-19 trials, 89% (781 subjects) at WHC. Of the 94% from whom race / ethnicity data were recorded, 21% were White Non-Hispanic, 47% were Black or African American Non-Hispanic, 24% were Hispanic and 8% were Other (Asian, American Indian, Alaska Native, or more than one race or ethnicity).

Number of Subjects

Approximately 40 subjects will be recruited at WHC and / or other MedStar hospital and / or critical / clinical care sites.

Recruitment Methods

A daily COVID-19 testing list is acquired from the laboratory network in the MedStar system and will be used for screening purposes. A designated central study coordinator will review the list and contact patients directly by phone. The same coordinator will also screen the EMR for COVID-19 patients being discharged from the ED in the past 24 hours at Franklin Square and Washington Hospital Center. A dedicated phone script will be used to recruit patients by phone. The consent will be emailed or provided through the e-consent platform, Interlace, and time allowed for the subject to review and for questions to be addressed. A dedicated homecare company will be available for home COVID-19 RT-PCR testing and screening blood draw if

needed. Completion of screening, randomization and enrollment will be at either MedStar Washington Hospital Center or MedStar Franklin Square. The patient will be required to attend the same center for all in-person follow-up visits and end of study visits.

